### ***Adverse Event Reporting Period***

The study period during which AEs must be reported is normally defined as the period from the initiation of any study procedures to the end of the study treatment follow-up. The start of study procedures is considered to be the point of consent. Any AEs which fit the protocol defined reportable events must be reported from the time of consent until study completion.

At each contact with the subject the investigator must seek information on AEs by specific questioning and, as appropriate, by examination. Information on protocol defined AEs should be recorded immediately in the source document and also in the appropriate AE module of the eCRF. All clearly related signs, symptoms and abnormal diagnostic procedure results should be recorded in the source document and grouped under one diagnosis, as appropriate. The clinical course of each event should be followed until resolution or until it is determined at the end of the study that the AE will not resolve.

## ***8.2 General Adverse Event Definitions***

Following is a list of general AE definitions. For the purposes of this study, only SAEs occurring in the perioperative period, excluding elective procedures at any time, as well as all AEs related to the operative site should be reported.

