Objective(s)	
Primary: To compare the rate of aseptic loosening of the Triathlon Tritanium Tibial Baseplate with rates reported in the literature for cemented tibial baseplates at 2 years postoperative.
 
Secondary Objectives: To assess the Kaplan-Meier survival curves of the Triathlon Tritanium Tibial Baseplate and Triathlon Tritanium Patella and compare them with those reported for cemented knee components in the literature. The overall revision rate will evaluate all-cause revision and removal rates of the Triathlon Tritanium Tibial Baseplate and Triathlon Tritanium Patella.
 
To compare functional scores and Patient Reported Outcomes (PROs) between Cohort 1 (cementless) and Cohort 2 (cemented) at 2 years postoperative. The following outcomes measures will be collected:
 

• 2011 Knee Society Score (2011 KSS)

• Oxford Knee Score (OKS)

• Short Form-12 (SF-12)

Additional Data Collection	

• Subject demographics and medical histories are collected (age, gender, primary diagnosis, BMI, comorbidities, medications used, smoking history, alcohol use, education level, employment status, confounding orthopedic problems, etc.).

• 2011 KSS, OKS and SF-12 will be presented with respect to improvement from preoperative scores for the cohorts according to their respective evaluation schedules.

• Assessment of radiographic outcomes using Anteroposterior (AP), Mediolateral (ML) and Merchant radiographs for the cohorts according to their respective evaluation schedules.

• A Follow-up Questionnaire is administered to assess patient satisfaction, pain, study device survivorship and capture adverse events (AEs) for the cohorts according to their respective evaluation schedules.

• Collection and evaluation of device related AEs and unanticipated adverse device effects (UADEs).

Number of Subjects	
A total of 500 cases will be enrolled in the study.
 
Cohort 1 (cementless): 356 cementless cases Cohort 2 (cemented): 144 cemented cases
 

• Cases must receive the appropriate study device to count toward enrollment.

**Diagnosis and Main  
Inclusion/Exclusion  
Criteria**

Inclusions:

1. Patient has signed an IRB/EC approved; study specific Informed Patient Consent Form.

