## **2.2 Safety**

All operative site events occurring at any time, as well as all serious adverse events (SAEs) occurring in the perioperative period (intraoperative to hospital discharge), are collected and compared to published data. It is expected that the AE rates reported for the Triathlon Tritanium Tibial Baseplate and Patella will be comparable to those reported in the literature for cemented primary total knee systems on the market. Details regarding AE definitions, recording and reporting are in Section 8 of this protocol, Adverse Events.

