## **8 Adverse Events**

### **8.1 Reporting of Adverse Events**

The AE reporting requirements for this study are as follows:

- All AEs that are operative site related, regardless of seriousness or time of occurrence.
- All AEs that meet the definition of serious and occur within the perioperative period (intraoperative to hospital discharge)

CONFIDENTIAL

[figure not shown]
This material is the property of Stryker Orthopaedics. Do not disclose or use except as authorized in writing by Stryker.

On postoperative functional evaluations, investigators and SCs are prompted to question subjects as to whether they have seen a doctor for any reason, been hospitalized for any reason or have a current impediment to their function.

Additionally, SCs are responsible for following up with the subjects regarding any questionable responses received on the Follow-up Questionnaire. If it is determined upon this further investigation that a protocol-defined AE has occurred, the SC will be responsible for completing an AE eCRF, submitting the event to Stryker and reporting to the IRB/EC, as required.

The following decision tree facilitates identification of AEs for which reporting is required under this study protocol:

Figure 2: Adverse Event Decision Tree

CONFIDENTIAL

This material is the property of Stryker Orthopaedics. Do not disclose or use except as authorized in writing by Stryker.

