### ***General Physical Examination Findings***

At screening for inclusion into the study, any clinically significant abnormality should be recorded as a preexisting condition and reported on the Demographics eCRF. From the time of consent forward, any new clinically significant findings or abnormalities that meet the definition of a protocol defined AE must also be recorded and documented as an AE.

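### The AE reporting rules contain no device-related or UADE class, so a device effect away from the knee after discharge is not reportable although the synopsis says such events are collected

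*Combined protocol and SAP*

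**What the plan says.** The Study Synopsis, under Additional Data Collection, lists "Collection and evaluation of device related AEs and unanticipated adverse device effects (UADEs"), with no limit of body site or time. Section 8.2 defines both the adverse device effect and the UADE, again without such a limit.

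Section 8.1 names two reportable classes:

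- The first goes by location: "All AEs that are operative site related, regardless of seriousness or time of occurrence".
- The second goes by seriousness and timing: "All AEs that meet the definition of serious and occur within the perioperative period (intraoperative to hospital discharge").

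Section 8.2 closes the list: to be reported are "only SAEs occurring in the perioperative period, excluding elective procedures at any time, as well as all AEs related to the operative site". Section 2.2 gives the same scope, pairing operative-site events at any time with the second class: "as well as all serious adverse events (SAEs) occurring in the perioperative period (intraoperative to hospital discharge").

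Section 8.3 asks for notice within 24 hours when the investigator considers an AE device related or is unsure. Its lead-in presents these as a subset of the AEs that are already reportable, and it later gives a two-week recommendation for the remaining reportable ones. UADEs are not mentioned in 8.3.

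Section 8.1 also refers to Figure 2: "The following decision tree facilitates identification of AEs for which reporting is required under this study protocol". The figure is not in the text available for this review.

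**The concern.** A trial that says it evaluates device-related AEs and UADEs needs a rule that brings them onto an AE form. Here the scope is set by location (the operative site) or by seriousness and timing (serious, up to discharge), and never by relation to the device. Relatedness is assessed on the AE form, so an event that never reaches a form is never assessed.

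Two things are at stake. First, the synopsis commitment is not met for part of the events it names. Secondly, sites may treat the same event differently: the 24-hour sentence in 8.3, read alone, sounds like a separate duty, while its lead-in and section 8.2 say otherwise, and the term operative site related is not defined.

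The sponsor's own documents show what kind of event is meant. Sections 12.2 and 12.3 list metal sensitivity reactions. The labeling in Appendix G describes wear debris leaving the joint and collecting in lymph nodes, with long-term effects unknown. It also says that no significant medical complications have been reported from these particles, so this is an example and not a rate.

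**Working it through.** The plan gives no figure to reproduce. The check sets the rules side by side and runs the possible events through them.

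**Where device relatedness or UADE appears**

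| Place | Content | Makes the event reportable? |
|---|---|---|
| Synopsis, Additional Data Collection | Device-related AEs and UADEs collected and evaluated | States the intent only |
| 8.1 | Two classes: operative site; serious up to discharge | Neither uses relatedness (0 of 2) |
| 8.2, opening | Restricts reporting to those classes | No |
| 8.2, definitions | Adverse device effect and UADE defined | Definition only |
| 8.3 | Relatedness triggers 24-hour notice, within reportable AEs | Timing only |
| 8.4 | Recording of protocol-defined AEs | No |
| Appendix F, AE form | Device-related item: Yes, No, Uncertain | Only once a form is opened |

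In the text reviewed, UADE occurs in three places: the abbreviation list, the synopsis and the definition in 8.2. It occurs in none of 8.1, 8.3 and 8.4.

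**Device-related events against the two classes**

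Cross site (operative or elsewhere), seriousness (yes or no) and time (operation to discharge, or later): 2 × 2 × 2 = 8 combinations.

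- Operative site: 4 combinations, all reportable under the first class.
- Elsewhere, serious, up to discharge: 1 combination, reportable under the second class.
- Elsewhere, non-serious up to discharge; elsewhere, serious after discharge; elsewhere, non-serious after discharge: 3 combinations, in neither class.

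So 4 + 1 = 5 combinations are reportable and 8 − 5 = 3 are not. UADEs are serious by definition, so for them only site and time vary: 2 × 2 = 4 combinations, of which one (elsewhere, after discharge) is in neither class. These are kinds of event, not frequencies.

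**What happens to an event in neither class**

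Seven places tie recording or tabulation to protocol-defined AEs:

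1. 8.1, questionnaire follow-up: "If it is determined upon this further investigation that a protocol-defined AE has occurred, the SC will be responsible for completing an AE eCRF".
2. 8.1, General Physical Examination Findings: new findings "that meet the definition of a protocol defined AE must also be recorded and documented as an AE".
3. 8.1, Adverse Event Reporting Period.
4. 8.4.
5. 9.2.1.
6. 9.2.2.
7. The first question of the Post-op Functional Evaluation form in Appendix F.

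The event may still be noted. Section 8.1 requires questioning about AEs at each contact, the Post-op Functional Evaluation has free text for other medical events since the last visit, and 9.4.1 plans AE lists from the Follow-up Questionnaire. But the free-text section has no relatedness field, and the questionnaire leads to an AE form only for a protocol-defined AE. The event is therefore not assessed for relatedness and is not in the 9.2.2 table.

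**Can the AE form take these events?**

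The form lists codes a to z (26) and aa to kk (11), 37 in all. By their order and labels the last 11 lie outside the operative site: 11/37 = 29.7%. The form also has a post-operative timing option and the three-way device-related item. The form has room for these events; the rule for opening it does not include them.

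**The case against.** The strongest case is that this is a wording mismatch in a deliberately narrow post-market scope.

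- **Figure 2 is unseen.** It belongs to 8.1 and may have a device-related branch. That stands as a limit. But such a branch would conflict with the restrictive sentence in 8.2 and with 2.2, so the text would still need alignment.
- **Section 8.3 states the duty.** Read alone, its device-related sentence requires notice and an AE form within 24 hours, and a UADE, being device associated, would fall under it. The lead-in limits the whole list to reportable AEs, so the plain reading goes the other way. What stands is that the section is ambiguous.
- **The synopsis may mean relatedness among the AEs collected.** It does not say all. That reading is possible, but a separate item naming UADEs is a weak way to express it.
- **Operative site related may be causal.** The implant sits at that site, and the first group of form codes includes peroneal nerve palsy and reflex sympathetic dystrophy. Against this, the form separates other operative-site events from other systemic ones. The term is undefined, which is part of the problem.
- **Other routes exist.** Section 8.3.1 sends AE reports to the IRB or EC under its own rules, 8.5 provides sponsor investigation of events entered as Product Experience Reports, and the clearance letters recall medical device reporting. None of these requires a study AE form or a relatedness assessment.
- **The seven places repeat one definition.** True; they show that no later rule widens the scope, not seven separate faults. Section 9.2.1 says its parameters include these AEs, and 9.2.2 does not expressly exclude others, but nothing provides for tabulating them as AEs.
- **The effect is small.** Probably so, and the importance is set accordingly.

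**Conclusion.** The concern holds. On the plain reading, sections 2.2 and 8.1 to 8.3 do not require reporting of a device-related AE or UADE that is unrelated to the operative site and occurs after discharge. A non-serious device-related AE away from the site before discharge is missed as well. The synopsis says that device-related AEs and UADEs are collected, so the passages must be reconciled.

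The gap lasts to 10 years in Cohort 1 and 5 years in Cohort 2. The documents give no basis for the number of events, which may be small because most device-related knee events are at the operative site. Those events, and the primary endpoint, are unaffected. Importance is low to moderate, but the change is cheap and should be made.

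The conclusion assumes that Figure 2 adds no device-related branch, that the lead-in to 8.3 governs the list below it, and that operative site related refers to location. Confidence is medium for these reasons. If any of the three is wrong, the gap narrows or closes, but the text still needs to be made consistent.

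**What to change.** 1. Add a third reportable class to 8.1, with the same words in 8.2: any AE, at any site and any time, that the investigator considers device related or is uncertain about, and any UADE.
2. State in 8.1 whether operative site related includes implant-caused events elsewhere in the body.
3. Name UADEs in 8.3 under the existing 24-hour device-related trigger.
4. Align 2.2, the first question of the Post-op Functional Evaluation form, and Figure 2 if it lacks the class.
5. Check that 9.2 follows. It points to 8.1 for protocol-defined AEs, so it should need no change of its own.

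If the sponsor wants to keep the narrow scope, the alternative is to limit the synopsis statement and the device-related sentence in 8.3 so that both match 8.1.

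The cost is wording in four sections (2.2, 8.1, 8.2 and 8.3), a check of Figure 2 and of 9.2, and one form prompt. The AE form needs no new fields. In conduct, expect a few extra AE forms, and some relatedness judgments in years when follow-up is by mail, online or telephone and the subject is not examined.

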### ***Adverse Event***

An **AE** is any untoward medical occurrence in a clinical investigation subject, which changes the medical baseline of the subject. An AE can be an unfavorable and unintended sign, symptom or disease, whether or not related to the study device (AEs may also be referred to as complications). See Section 8.1, Reporting of Adverse Events, for the AE reporting requirements for this study.

### ***Anticipated Adverse Event***

An **anticipated AE** is an AE, of which the nature, severity or degree of incidence is known and identified in applicable product labeling, published literature or the study protocol. The list of anticipated events is provided in Section 12, Risk/Benefit Assessment.

### ***Serious Adverse Event***

A **SAE** meets one or more of the following definitions:

- Resulted in in-patient hospitalization
- Resulted in prolonged existing hospitalization
- Resulted in persistent or significant disability/incapacity
- Resulted in permanent impairment of a body function or permanent damage to a body structure
- Necessitated medical or surgical intervention to preclude permanent impairment of a body function or permanent damage to a body structure
- Was a life-threatening situation
- Resulted in patient death

### ***Adverse Device Effect***

An **adverse device effect (ADE)** is a negative change in the subject's health that may have been caused by, or associated with, the use of the device.

### ***Unanticipated Adverse Device Effect***

An **unanticipated adverse device effect (UADE)** is any serious adverse effect on health, safety or any life-threatening problem or death caused by, or associated with, a device if that effect is a problem or death not previously identified in nature, severity or degree of incidence, or any other unanticipated serious problem associated with a device and related to the rights, safety or welfare of subjects.

## ***8.3 Study Sponsor Notification by Investigator***

Of reportable AEs, certain events must be submitted to Stryker within 24 hours for timely notification:

***Adverse events that require time sensitive reporting:***

An AE should be reported to Stryker Clinical Research either by telephone/fax/email within 24 hours of the site becoming aware of the event if any of the following apply:

- The AE is considered by the investigator to be device related or if the investigator is uncertain regarding the device related assessment;
- The AE required a reoperation of the study knee or a revision of any study knee components.

An AE eCRF must be completed within 24 hours. If a SAE occurs during the perioperative period, the de-identified source documentation must be uploaded to the appropriate location within Stryker's Electronic Data Capture (EDC) system within 24 hours of the investigative center's SAE awareness. See Section 11, Data Management, for additional details of Stryker's EDC system. These reports will be evaluated by Stryker to determine if a PER is required.

It is recommended that all other reportable AEs are submitted through eCRF entry within 2 weeks of becoming aware of the event.

At the time of the initial report, the following information should be provided:

• Subject number

• A description of the event

• Date of onset

• Current status

	

• Whether study treatment was discontinued

• Investigator assessment of the association between the event and the study treatment

--	---

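### Seriousness does not trigger 24-hour notice to the sponsor, so a serious operative-site event after discharge that is judged unrelated and not reoperated has only a recommended 2-week limit

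*Combined protocol and SAP*

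**What the plan says.** Section 8.1 decides which events are reportable. Operative-site events always are: "All AEs that are operative site related, regardless of seriousness or time of occurrence". Other events are reportable only if they are serious and occur between surgery and hospital discharge. Section 8.2 defines serious in the usual way, including death, admission, permanent impairment and "Was a life-threatening situation".

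Section 8.3 then sets the timing for reportable events, in this order:

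- Notice by telephone, fax or email: "An AE should be reported to Stryker Clinical Research either by telephone/fax/email within 24 hours of the site becoming aware of the event", if either of two conditions applies.
- First condition: "The AE is considered by the investigator to be device related or if the investigator is uncertain regarding the device related assessment".
- Second condition: "The AE required a reoperation of the study knee or a revision of any study knee components".
- A 24-hour limit for completing the AE eCRF, stated as mandatory, with no indication of which AEs it covers.
- A 24-hour rule for serious events before discharge: "If a SAE occurs during the perioperative period, the de-identified source documentation must be uploaded" to the sponsor's data-capture system.
- A statement that the sponsor will assess these reports to decide whether a PER is needed.
- The residual rule: "It is recommended that all other reportable AEs are submitted through eCRF entry within 2 weeks of becoming aware of the event".

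The draft AE form in Appendix F follows the same logic. Its 24-hour contact prompt is attached to the device-relatedness item, and the seriousness item carries no deadline.

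**The concern.** For events after discharge, how fast the sponsor hears about a serious event depends on the site's own relatedness rating unless the knee is reoperated or revised. That rating also affects escalation. Under Section 8.5 the investigator oversees safety at the center, and the sponsor formally investigates the AEs that enter its PER system. The draft AE form makes PER filing compulsory only when relatedness is yes or uncertain.

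Deep joint infection, tibial fracture and patella fracture are all listed on the draft AE form. Section 12.2 attributes postoperative fracture to trauma, bone defects or poor bone stock, so an investigator could reasonably rate one as unrelated. The same section names infection and trauma among the causes of late loosening, and tibial baseplate revision for aseptic loosening is the primary endpoint. Whether a serious event is an unanticipated adverse device effect also turns on its association with the device. A second look by the sponsor is therefore most useful where the site has answered no.

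**Working it through.** No formula applies, and the plan states no figure to reproduce. The check is to apply the Section 8.3 rules to each combination of seriousness, timing, relatedness and reoperation or revision, for events reportable under Section 8.1.

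1. **Related or uncertain, or reoperated or revised, serious or not.** A trigger is met, so 24-hour notice applies.
2. **Serious, before discharge, unrelated, no reoperation or revision.** Neither trigger is met. Source-document upload within 24 hours is mandatory because the event is serious. The eCRF deadline is unclear.
3. **Serious, operative site, after discharge, unrelated, no reoperation or revision.** Neither trigger is met, and the upload rule does not apply because the perioperative period ends at discharge. The recommended 2 weeks is what remains.
4. **Non-serious, operative site, unrelated, no reoperation or revision.** The recommended 2 weeks applies.

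Cases 3 and 4 are treated alike, although one is serious and the other is not.

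The result for case 3 depends on how far the 24-hour eCRF sentence reaches. There are three possible readings:

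- **It covers every reportable AE.** Case 3 would then have a 24-hour form deadline, but the 2-week sentence would have no events left to govern. This reading is hard to sustain.
- **It covers only the events on the two-item list.** Case 3 has the recommended 2 weeks. Case 2 has a mandatory upload but no clear form deadline.
- **It covers the list plus serious events before discharge.** Case 2 has 24 hours for both actions. Case 3 still has the recommended 2 weeks.

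The gap in case 3 therefore remains under both readings that leave the 2-week sentence with a purpose. The difference in time is 14 − 1 = 13 days, between a 24-hour rule and a recommendation.

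Other wording adds to the uncertainty. The opening of Section 8.3 says that certain events must reach the sponsor within 24 hours, while the trigger sentence says should. The reporting-period text in Section 8.1 says that protocol-defined AEs should be entered at once in the source record and the AE module of the eCRF. A site thus has three timings for form entry: at once, 24 hours and 2 weeks.

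**The case against.** The strongest reply is that the gap is narrow. An event must be serious, at the operative site, after discharge, not reoperated or revised, and positively rated unrelated, since uncertain already triggers notice. A fracture or deep infection that goes back to theater meets the second trigger. An unanticipated adverse device effect is device-associated by definition, so the first trigger covers it once the site rates it related or uncertain. The devices are cleared and the study is post-market with deliberately limited AE collection. No interim analysis is planned (Section 9.4.3), and multi-center results are to be published at 2, 5 and 10 years (Section 16), so a 13-day delay alters no planned analysis. All of this stands. It limits the consequence to prompt safety review and does not close the gap.

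Section 8.1 also asks for immediate entry, and Section 8.3.1 requires reports to the ethics committee or IRB under its own rules. The first is only a should and is not a notification to the sponsor. The second goes to a different body.

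Three stronger readings are tempting, and the documents do not support them:

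- **That seriousness plays no part in any 24-hour rule.** Before discharge it does, because seriousness alone makes the source-document upload mandatory.
- **That a serious event before discharge is under two conflicting deadlines.** One rule concerns document upload and the other form entry, so both can be met. The 2-week sentence also comes after the upload rule and covers all other events, which most naturally leaves these out. The defect is ambiguity.
- **That the number of affected events can be estimated.** The documents give no rate for events of this kind, and any count would rest on an assumed one.

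**Conclusion.** The point holds for serious operative-site events after hospital discharge that the investigator rates unrelated and that need no reoperation or revision. These have a recommended 2-week eCRF limit where other events have 24 hours, and they fall outside the reports that Section 8.3 says will be assessed for a PER. This assumes that the 24-hour eCRF sentence does not cover every AE, which is the only way to leave the 2-week sentence any content.

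For serious events before discharge the finding is weaker: the upload duty is clear, but they are not on the trigger list and their form deadline cannot be determined. The number of events concerned is unknown. No estimate, test or planned analysis is affected. This is a cheap improvement to safety reporting.

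**What to change.** In Section 8.3, add a third item to the 24-hour list: *The AE is reportable under Section 8.1 and meets any definition of serious in Section 8.2, whether or not considered device related.* State that the 24-hour eCRF sentence applies to every event on that list. Make the 2-week limit mandatory for the remaining reportable AEs.

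Then align the related text: the must and should wording within Section 8.3, the immediate-entry wording in the reporting-period part of Section 8.1, and the 24-hour prompt on the draft AE form in Appendix F, which should also appear at the seriousness item.

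Because Section 8.3 applies only to events that are already reportable, this changes timing and does not widen AE collection. The cost is a few lines of protocol and form text and a few more 24-hour reports per site.
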